4.3. Exploratory Endpoints

- Time since randomization until improvement in oxygenation, (defined as independence from supplemental oxygen) during 28-day assessment period (or discharge, whichever comes earlier)**
- Number of days with hypoxia defined as SpO₂ < 93% breathing room air or the dependence on supplemental oxygen after randomization to Day 28 (or discharge, whichever comes earlier)**
- Time since randomization until absence of last fever (defined as 37.1°C or more) for more than 48h without antipyretics**
- **change in CRP levels between day 1 and day 6, and between day 1 and day 15 (or discharge in each case**
- **change in ferritin levels between day 1 and day 6, and between day 1 and day 15 (or discharge in each case).**
- Incidence of SARs/SUSARs during 28 days**
- Duration of hospital stay**
- Duration of hospital stay in survivors**
- **Change from baseline in 6-point ordinal scale to Day 6, Day 15 and D28 (by phonecall) post randomization**

- Percentage of participants reporting at least a 2-point improvement sustained to D28 or discharge
- AUEC/Time using the 6-point score recorded daily – up to D15, D28 and all data recorded
- Percentage of participants who record a 2-point improvement from baseline or discharge at D6, D15 and D28
- Percentage of participants not deteriorating according to the ordinal scale by 1 or 2 points on D6, D15 and D28
- 6-point Ordinal Scale at 6 and 15 days (or discharge whichever comes first) and day 28 (phone call), in relation to serum D-dimers and complement C5a levels at baseline

- Time since randomization until first use of high-flow oxygen devices or non-invasive mechanical ventilation or invasive mechanical ventilation or ECMO in non-ventilated patients (i.e. excluding patients who are ventilated within 24h prior to or after randomization) during 28-day assessment period
- duration of ventilator-free days after randomization to Day 28 (or discharge, whichever comes earlier)
- Duration of invasive mechanical (including ECMO) and non-invasive mechanical ventilation in ventilated patients
- Duration of ICU stay in patients that enrolled in trial on invasive or non-invasive mechanical ventilation for less than 24h prior to or after randomization during 28-day assessment period
- Duration of ICU stay in patients that enrolled in trial that were on invasive or non-invasive mechanical ventilation or high-flow oxygen devices within 24h prior to or after randomization during 28-day assessment period
- Time since randomization to progression to ARDS
criteria-defined ARDS according to the adapted Berlin criteria as follow:
 - * Within 1 week of a known clinical insult or new or worsening respiratory symptoms
 - * bilateral infiltrates not supposed to be of cardiac origin or fluid overload
 - * $\text{PaO}_2/\text{FiO}_2 < 300$ mmHg
 - * $\text{PEEP} > 5$ cm H₂O on invasive or non-invasive ventilation or flow ≥ 50 L/min on HFOT (Optiflow)
- Time since randomization to progression to ARDS according to D-dimers and complement C5a at randomization
- Incidence of lung function abnormalities at follow up 12-22 weeks post-randomization
- Incidence of lung fibrosis on chest high-resolution computed tomography (HRCT) scan at follow up 12-22 weeks post-randomization

4.4. Pharmacodynamic and Pharmacokinetic endpoints (exploratory)

Pharmacodynamic endpoints:

Plasma and serum samples will be collected for summary and exploratory analysis as appropriate, may include but are not limited to (see also Section 9.3):

- ADA – D1 and long-term follow-up from serum samples (Summary only to indicate presence or not)
- Local safety labs such as D-dimers, LDH, ferritin, CRP, fibrinogen
- Complement system assessment (EDTA tubes) – D1, D2, D6 and D15 (or at hospital discharge, if earlier)

[figure not shown]
- Cytokines and biomarkers (from selected centres) on D1, D6 and D15 (or at hospital discharge, if earlier)
 - o Cytokines may include, but not limited to:
 - IL-1beta, IL-1RA, IL-2, IL-8, IL-6, TNFa, GM-CSF, G-CSF, IP-10, MCP-1, MIP-1a, IFNg, and IL-10
 - o Biomarkers may include but not limited to
 - sRAGE, Angiopoietin-2), KL6
- DNA for pharmacogenomic research (Paxgene tube, D1 only)

Pharmacokinetic endpoints:

Blood samples will be taken from participants in Arm A only on D1, D2, D6 and day 15/discharge– all pre-dose.

5. Study design

5.1. Description of study design

This investigator-initiated trial is a phase 2 academic, prospective, 2:1 randomized, open-label, multi-center interventional study designed to investigate the efficacy of subcutaneous Zilucoplan® in improving oxygenation and short- and long-term outcome of COVID-19 patients with acute hypoxic respiratory failure. There are currently no treatments reducing lung damage in COVID-19 patients, and no treatment that attempts to halt the progression from manageable acute hypoxic respiratory failure to acute lung injury or ARDS in patients with COVID-19 infection. **Justification for our objective** is that preventing progression from early acute hypoxic respiratory failure to ARDS could have a huge impact on the foreseeable overflow of the ICU units, that is already happening in some countries and is bound to happen on a global scale.

Several academic and non-academic centers in Belgium will participate in this trial. Study coordination, monitoring and data management will be performed under the responsibility of the Health Innovation and Research Institute UZ Ghent (HIRUZ) Clinical Trial Unit and Data Management Unit.

The **hypothesis of the proposed intervention** is that Zilucoplan® has profound effects on inhibiting acute lung injury induced by COVID-19, and can promote lung repair mechanisms, that lead to a 25%

improvement in lung oxygenation parameters. This hypothesis is based on experiments performed in mice showing that C5a blockade can prevent mortality and prevent ARDS in mice with post-viral acute lung injury.

We will randomize patients with confirmed COVID19 with acute hypoxic respiratory failure (1. O₂ saturation below 93% on minimal 2l/min O₂ therapy; and/or 2. PaO₂/FiO₂ below 350 mmHg) to receive up to 14 days of SC Zilucoplan® on top of standard of care (active group A), or to receive standard of care treatment (control group B). Randomization will be done at a 2:1 ratio active: control group. In the active group A, patients will additionally receive daily antibiotics (daily 3rd generation cephalosporin IV while in hospital, followed by oral ciprofloxacin while discharged) as primary prophylaxis against meningococcal disease until 14 days after the last dose of Zilucoplan®. Control group B will receive standard of care and prophylactic antibiotics (3rd generation cephalosporin IV) for only 1 week (or until hospital discharge whichever comes first), to control for the effects of antibiotics on the clinical course of COVID-19. In case of allergies to these antibiotics, or on clinical indication, these antibiotics may be switched to antibiotics that also cover *Neisseria meningitidis*.

To measure the effectiveness of Zilucoplan® on restoring lung homeostasis, the **primary endpoint** of this intervention is **measuring change in oxygenation parameters** comparing baseline values (pretreatment) to values predose day 6 and to values at day 15 (or discharge whichever comes first) post-randomization in group A and group B and the differences in these values between group A and group B.

5.2. End of Study Definition

5.2.1. For an individual subject

The subject has completed the study if he or she has completed all phases of the study, including the last visit (week 12-22 post-randomization clinical follow up visit) or the last scheduled procedures, as described in this protocol (see section “9. Study Specific Procedures”).

5.2.2. For the whole study

Overall, the end of the study is reached when the last study procedure for the last subject has occurred: last subject, last visit (LSLV).

As soon as the whole study has ended (cfr. the definition above), the coordinating investigator shall notify the HIRUZ Clinical Trial Unit, so that the Competent Authority and the Ethics Committee can be informed in a timely manner according to the regulatory requirements (within 90 days after end of the study, or if the study had to be terminated early, this period must be reduced to 15 days and the reasons should clearly explained).

5.3. Estimated duration of the study

We estimate the study to terminate in 52 weeks, including last clinical follow up visits.

6. Inclusion and Exclusion Criteria

6.1. Inclusion Criteria

-Recent (≥ 6 days and ≤ 16 days of flu-like symptoms or malaise prior to randomization) infection with COVID-19.

-COVID-19 diagnosis confirmed by antigen detection test and/or PCR and/or positive serology, or any emerging and validated diagnostic laboratory test for COVID-19 within this period. For patients with a negative SARS-CoV-2 PCR and either a positive SARS-CoV-2 antigen or antibody test, the presence of suggestive lesions for COVID-19 on chest-CT scan is mandatory.

-In some patients, it may be impossible to get a confident laboratory confirmation of COVID-19 diagnosis after 24h of hospital admission because viral load is low and/or problems with diagnostic sensitivity. In those cases, in absence of an alternative diagnosis, and with highly suspect bilateral ground glass opacities on recent (< 24 h) chest-CT scan (confirmed by a radiologist and pulmonary physician as probable COVID-19), and a typical clinical and chemical diagnosis with signs of cytokine release syndrome, a patient can be enrolled as probable SARS-CoV-2-infected. In all cases, this needs confirmation by later seroconversion.

-Presence of hypoxia defined as

1) O₂ saturation below 93% on minimal 2l/min O₂ therapy;
and/or

2) PaO₂/FiO₂ below 350 mmHg (Strongly recommended: patient in upright position, after minimal 3 minutes without supplemental oxygen; In ventilated patients PaO₂ can be taken from invasive arterial line and FiO₂ taken directly from mechanical ventilation settings).

-Signs of acute lung injury and/or cytokine release syndrome defined as

ANY of the following

-serum ferritin concentration > 1000 mcg/L and rising since last 24h

-single ferritin above 2000 mcg/L in patients requiring immediate high flow oxygen device (Optiflow) or non-invasive or invasive mechanical ventilation

-lymphopenia defined as < 800 lymphocytes/microliter and two of the following extra criteria

-Ferritin > 700 mcg/L and rising since last 24h

-increased LDH (above 300 IU/L) and rising since last 24h

-D-Dimers > 1000 ng/mL and rising since last 24h

-CRP above 70 mg/L and rising since last 24h and absence of bacterial infection

-if three of the above are present at admission, no need to document 24h rise

-Low dose Chest CT or HRCT or Angio Chest CT scan showing bilateral infiltrates within last 2 days prior to randomization

-Admitted to specialized COVID-19 ward or an ICU ward taking care of COVID-19 patients

-Age ≥ 18 years

- Women of childbearing potential must have a negative serum pregnancy test pre-dose on day 1. Women of childbearing potential must consistently and correctly use (during the entire treatment period and 4 weeks after last Zilucoplan® administration) at least 1 highly effective method for contraception.

Male subjects (who have not been surgically sterilized by vasectomy) must agree to use effective contraception during the study.

-Willing and able to provide informed consent or legal representative willing to provide informed consent

6.2. Exclusion Criteria

- Patients with known history of serious allergic reactions, including anaphylaxis, to Zilucoplan® or inability to receive antibiotic prophylaxis due to allergy to ALL of the antibiotics that can be given for prophylaxis of meningococcal disease
- History of active or past meningococcal disease
- Invasive mechanical ventilation > 24 h at randomization**
- Patient on ECMO at screening
- Clinical frailty scale above 3 before onset of the COVID-19 episode
- Weight below 54 kg as measured max 1 week prior to inclusion
- Weight above 150 kg as measured max 1 week prior to inclusion
- Active bacterial or fungal infection
- Unlikely to survive beyond 48h
- Neutrophil count below 1500 cells/microliter
- Platelets below 50.000/microliter
- Patients enrolled in another investigational drug study
- Patients on high dose systemic steroids (> 8 mg methylprednisolone or equivalent for more than 1 month) or other moderately immunosuppressive drugs (in the opinion of the investigator) for COVID-19 unrelated disorder
- Patients on current complement inhibiting drugs
- Serum transaminase levels >5 times upper limit of normal, unless there are clear signs of cytokine release syndrome defined by LDH >300 IU/L and ferritin >700 ng/ml
- Pregnant or breastfeeding females (all female subjects deemed of childbearing potential by the investigator must have negative pregnancy test at screening)

6.2.1. Screen failures

Screen failures are defined as subjects who consent to participate in the clinical study but are not subsequently randomly assigned to the study intervention or entered in the study. A minimal set of screen failure information will be kept to ensure transparent reporting of screen failure subjects.

7. Target Population

7.1. Subjects

7.1.1. Number of subjects and planned recruitment rate

The number of subjects that will be included in this study is: 81.

These are divided into following sub-groups: 54 patients will be randomized to receive daily Zilucoplan® SC for a maximum of 14 days plus prophylactic antibiotics (3rd generation cephalosporin IV, followed by oral ciprofloxacin, or appropriate alternative) daily, maintained for at least 2 weeks after last Zilucoplan® dose)(group A); 27 patients will be randomized to receive standard of care (Group B) plus one week (or until hospital discharge whichever comes first) of 3rd generation cephalosporin IV (or appropriate alternative).

The sample size calculation is elaborated in the Statistics section in section 11.

7.1.2. Withdrawal and replacement of subjects

Subjects are free to withdraw from participation in the study at any time upon request. If patient decides to leave hospital between day 6 and day 15, treatment with Zilucoplan® will be terminated, and day of discharge will be used to calculate the day 15 endpoint.

An investigator must discontinue or withdraw a subject from the study for the following reasons:

- allergic reactions (anaphylactic shock) to Zilucoplan® or antibiotic used for prophylaxis of meningococcal disease. Allergy to an antibiotic, should lead to a switch to another antibiotic so that patients receive prophylaxis against meningococcal disease for at least 14 days after the last dose of Zilucoplan®.
- Pregnancy
- Significant study intervention non-compliance
- If any clinical adverse event (AE), laboratory abnormality, or other medical condition or situation occurs such that continued participation in the study would not be in the best interest of the subject
- If the subject meets an exclusion criterion (either newly developed or not previously recognized) that precludes further study participation
- Cases included in the trial with a 'tentative' diagnosis of COVID-19 in which it is not possible to get a confident diagnosis by serology or other means later in the disease course, will be withdrawn from the study as soon as it is clear that SARS-CoV2 was not the cause of the clinical presentation.

In all cases, the reason why subjects are withdrawn must be recorded in detail in the eCRF and in the subject's medical records.

In all patients that have received Zilucoplan® as a study medication (group A patients), prophylaxis for meningococcal disease using either 3^d generation cephalosporin IV daily or oral ciprofloxacin daily (or appropriate alternative) should be continued for 14 days after the last Zilucoplan® dose, even if patient retracted from the study, or was withdrawn from the study by the investigator. In case reason for

withdrawal was allergy to an antibiotic, an alternative antibiotic for prophylaxis should be given until 14 days after the last Zilucoplan® dose.

The following actions must be taken if a subject fails to return to the clinic for a required study visit (visit at 12-22 weeks post-randomization):

- The site will attempt to contact the subject and reschedule the missed visit within 4 weeks and counsel the subject on the importance of maintaining the assigned visit schedule and ascertain if the subject wishes to and/or should continue in the study.
- Before a subject is deemed lost to follow-up, the investigator or designee will make every effort to regain contact with the subject (where possible, 3 telephone calls and, if necessary, a certified letter to the subject's last known mailing address or local equivalent methods). These contact attempts should be documented in the subject's medical record or study file.
- Should the subject continue to be unreachable, he or she will be considered to have withdrawn from the study with a primary reason of lost to follow-up.

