5 STUDY POPULATION CHARACTERISTICS

5.1 Participant disposition

Participants are considered **screenfails** if they were deemed not eligible for randomisation.

Since this is initially an in participant study the Nominal Days are not considered a scheduled protocol visit.

A participant who dies at any time during the study is considered as having **completed the study and primary assessment period**. If they discontinued early from planned active treatment duration (i.e. not including hospital discharge), the participant is considered as having **completed the study and primary assessment period, but not completed planned active treatment duration**.

In addition, a participant is considered to have **completed the study** if they have completed D28 and the follow-up visit. Participants can be discharged from hospital at any time, and as long as they have completed D28 and the follow-up visit, they have **completed the study**.

Participants have **completed primary assessment period** if they have:

- Arm A: completed up to 14 days of treatment with study drug followed by 14 days of either IV or oral prophylactic antibiotic treatment (as an in-participant or after discharge from hospital) AND completed D28 procedures
- Arm B: Completed up to 14 days of treatment with study drug (SOC+ 1 week of prophylactic antibiotic treatment) AND completed D28 procedures

Participants have **not completed primary assessment period**:

- are discontinued treatment prior to end of planned active treatment duration due to an adverse event - they may still complete D28 and/or follow-up visits
- discontinue treatment prior to end of planned active treatment duration as they meet an exclusion criterion (either newly developed or not previously recognized) that precludes further study treatment participation - they still may complete D28 and/or follow-up visits
- withdraw consent from being treated prior to end of planned active treatment duration – they may agree to complete D28 and/or follow-up visits
- Complete the treatment as planned but do not complete D28 procedures

Participants have prematurely **withdrawn from the study** if they:

- are lost to follow-up, after hospital discharge (i.e. do not complete D28 and follow-up visits or do not complete follow-up visit).
- Withdraw consent from being treated prior to end of planned active treatment duration and from D28 and follow-up visits

-

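### Protocol 7.1.2 does not separate stopping study drug from leaving the study and requires no outcomes after an investigator withdrawal, although dosed patients stay in the analysis

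*Protocol*

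**What the plan says.** **Protocol.** Section 7.1.2 states: "An investigator must discontinue or withdraw a subject from the study for the following reasons". Six reasons follow: allergic reaction to the drug or the antibiotic, pregnancy, significant non-compliance, an adverse event or other condition that makes participation contrary to the subject's interest, an exclusion criterion "that precludes further study participation", and a tentative COVID-19 diagnosis that is not borne out. Patients in the last group "will be withdrawn from the study as soon as it is clear that SARS-CoV2 was not the cause of the clinical presentation". They may already have been dosed, because section 6.1 lets probable cases enrol without laboratory proof: "In all cases, this needs confirmation by later seroconversion".

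After withdrawal, 7.1.2 asks for two things: the reason on record and, in Arm A, prophylaxis for 14 days after the last dose. The contact steps in the same section concern a missed week 12-22 visit: "Before a subject is deemed lost to follow-up, the investigator or designee will make every effort to regain contact with the subject".

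**SAP.** Section 5.1 counts adverse-event cases as having stopped treatment, and adds that "they may still complete D28 and/or follow-up visits". It does the same for an exclusion criterion, now worded "that precludes further study treatment participation". Its list of premature study withdrawals holds only participants who "are lost to follow-up, after hospital discharge" and those who withdraw consent. Section 4.2 expects measurements to go on after study treatment stops. Sections 3.5.3 and 3.5.4 put every dosed participant in the Safety Set and the FAS. Protocol 4.2 defines mortality at D28 and at week 12-22 on all treated participants.

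**The concern.** The site works from the protocol and the statistician from the SAP, and the two describe different follow-up for the same patient. A site that reads 7.1.2 literally can end all study contact with a dosed patient, and no protocol text then asks for the D28 call or the final visit. A patient who merely misses the last visit must be pursued, while one withdrawn by the investigator need not be.

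The analysis cannot repair this later. Depending on the endpoint, the SAP gives such a patient ordinal score 7 for withdrawn, censors the time to response, counts a non-responder, or sets the value to missing (section 8.2 and Table 8.1). The mortality logistic regression in Table 8.1 states no rule for unknown status. At stake are the ordinal scale and mortality at D28 and week 12-22, in patients who remain in the denominator.

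**Working it through.** **1. The two documents side by side**

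| Reason | Protocol 7.1.2 | SAP 5.1 |
|---|---|---|
| Adverse event or condition | Discontinue or withdraw from the study, if participation is against the subject's interest | Treatment stop; later visits allowed |
| Exclusion criterion met | Discontinue or withdraw, if it precludes study participation | Treatment stop, if it precludes treatment; later visits allowed |
| Not COVID-19 | Withdrawn from the study | No category |
| Non-compliance | Discontinue or withdraw | No category |
| Pregnancy, allergy | Discontinue or withdraw | Not named; an allergic reaction could be counted as an adverse event |

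The SAP cites protocol version 3.0, but version lag is an unlikely explanation. The amendment log lists the not-COVID-19 reason ahead of the version 3.0 entry.

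**2. What protects vital status**

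Death is an SAE (Protocol 13.1). SAEs are reported over the whole study period (13.2.2). AEs are recorded to the end of the study, with special attention to those who left it for an AE (13.2.1). SAP 10.2, however, stops AE recording at early study discontinuation. None of these sections says that a patient withdrawn by the investigator is contacted again. A death that the site hears of would be reported, but nothing makes the site ask.

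**3. The plan's nearest figure**

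The plan gives no count of withdrawals. It does assume dropout below 10% in its power statement (Protocol 11.1): above 85% power with 54 and 27 patients, difference 80, SD 105, two-sided 5%. At 10% dropout the arms hold 48.6 and 24.3:

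- Power = Φ(80 / (105 × √(1/48.6 + 1/24.3)) − 1.96) = Φ(3.07 − 1.96) = 86.6%. The t-based value is 85.7%.

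The figure reproduces. It concerns PaO2/FiO2 at D6 and D15 and is untouched by this point.

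**4. Size of a loss at D28**

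Let a patients in Arm A and b in Arm B have unknown status. The Arm A death proportion can then lie anywhere in an interval of width a/54, and Arm B's in one of width b/27. The best-to-worst-case range of the difference has width a/54 + b/27. All counts below are assumed.

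- One in A: 1/54 = 1.9 points.
- One in B: 1/27 = 3.7 points.
- Two in A, one in B: 2/54 + 1/27 = 7.4 points.

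For comparison, the full 95% interval width for the mortality difference, with the same mortality p in both arms, is 2 × 1.96 × √(p(1−p)(1/54 + 1/27)). The values of p come from Protocol 2.2:

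- p = 7%: 23.6 points, so 7.4 is 31% of it.
- p = 20%: 37.0 points, so 7.4 is 20% of it.
- p = 40%: 45.3 points, so 7.4 is 16% of it.

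**5. Can the dropout figure cap this?**

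Ten percent of 81 is 8.1, so take 8 patients. All in A gives 8/54 = 14.8 points. Six in A and two in B gives 18.5. All in B gives 8/27 = 29.6. The answer depends on an unknown split, and the 10% is a planning assumption for another endpoint at earlier days. It is not a cap.

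**The case against.** The best defence is that 7.1.2 says discontinue or withdraw, which are alternatives, and that Protocol 8.1.4 shows a drug-only stop for anaphylaxis or severe AE. A sensible site could stop the drug and keep the patient. That reading is open, but the stated object is the study, nothing tells the site which applies, and the not-COVID-19 reason leaves no choice.

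A reader might infer that protocol and SAP contradict each other outright. They do not. SAP 5.1 only permits later visits, and it defines disposition categories rather than instructing sites. Table 8.1 also anticipates withdrawal for any reason and censors those withdrawn from treatment or study. The mismatch lies in study status and in the data that SAP 4.2 expects.

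A reader might also infer that deaths will go unrecorded. SAE reporting covers part of that gap, so the clearer loss is the ordinal scale.

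Three further points stand. The not-COVID-19 group is narrow: Protocol 6.1 demands a typical CT read by two specialists, a typical clinical and chemical picture, and no alternative diagnosis. Protocol 7.2 expects high retention. The endpoints concerned are secondary, get no p-values (SAP 3.1) and are treated as exploratory (SAP 4.5).

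**Conclusion.** The point holds as a gap in the instruction to sites. Section 7.1.2 merges two different actions, mandates study withdrawal for one group that may already be dosed, and asks for no outcome afterwards, while the analysis keeps those patients. D28 and week 12-22 ordinal-scale data can be lost, and vital status is only partly protected.

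The size is 1.9 points of extra range in the D28 mortality difference per unknown Arm A patient and 3.7 per unknown Arm B patient. This rests on 54 and 27 dosed patients. The number lost is unknown, and no upper bound can be drawn from the documents. The direction of any bias is also unknown; a Zilucoplan allergy can arise only in Arm A, but nothing shows which way that would act. With the few losses that seem likely, the effect is probably small beside sampling error. No claim is made about the primary endpoint or about a number of lost AEs. This is a cheap improvement.

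**What to change.** - **Protocol 7.1.2:** by default, the listed reasons stop study drug only. The investigator may still end study procedures that are against the patient's interest. For every dosed patient, including those later found not to have COVID-19, collect the D28 ordinal-scale and (S)AE call and vital status at D28 and week 12-22, unless consent to follow-up is withdrawn.
- **SAP 5.1:** add the not-COVID-19 and non-compliance cases to the treatment-discontinuation list.
- **SAP 10.2:** align the end of AE recording with Protocol 13.2.

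The D28 call already asks for the ordinal scale and (S)AEs (Protocol 9.2), and the final visit already exists, so no new procedure is needed. The cost is a protocol amendment with ethics approval (Protocol 15.3.2), two SAP edits, and slightly longer follow-up of a few patients.
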